11.1. Adverse Events

Per the study protocol all adverse events (AE) occurring during the study, whether or not attributable to study drug, will be recorded in the subject's source documents and CRF. Adverse event reporting will start at the date of informed consent and continue through the end of study (Week 8 visit).

AE severity will be assessed by the Investigator as mild, moderate or severe. The Investigator will also assess the relationship of each AE to study drug (none, unlikely, possible, probable, definite). Treatment-related AEs are defined as events the Investigator considers to be possibly, probably, or definitely related to study drug, as well as events with “unknown” relationship.

Adverse event summaries will present data by treatment arm.

An overall summary of adverse events will be provided that reports, for each treatment arm, both the number (%) of events meeting a specific criterion and the number (%) of subjects with at least one event meeting that criterion. Events meeting the following specific criteria will be presented in this table:

- Any reported adverse event (i.e., both pre-existing and treatment-emergent events)
- For treatment-emergent AEs:
 - Any TEAE
 - Any serious TEAE
 - TEAEs by severity (mild, moderate, severe)
 - TEAEs by relationship (none, unlikely, possible, probable, definite)
 - TEAEs by relationship (not related, related)
 - TEAEs by action taken with study drug (dose increased, dose not changed, dose reduced, dose interrupted, drug withdrawn, not applicable, unknown)
 - TEAEs by outcome (recovered no sequelae, recovered with sequelae, ongoing, death)

In addition to the overall summary, the following summaries of the number (%) of subjects with at least one TEAE will be produced:

- Incidence by SOC and PT, in alphabetical order of SOC and PT, for both all TEAE and related TEAE
- Incidence by PT, in decreasing frequency of PT, for both all TEAE and related TEAE
- Incidence of TEAEs that resulted in dose reduction or discontinuation of study drug (i.e., action taken with study drug reported as dose reduced, dose interrupted, or drug withdrawn), in decreasing frequency of PT
- Incidence of TEAE by PT and severity (mild, moderate, severe), in alphabetical order of SOC and PT
- Incidence of TEAE by PT and relationship (yes, no), in alphabetical order of SOC and PT
- Kaplan-Meier figure of time to first treatment-emergent adverse event (i.e., time from date of randomization to earliest TEAE start date) by treatment arm.

In these summaries, if a subject experiences the same AE (preferred term) multiple times that subject will be counted only once for that preferred term. Similarly, if a subject experiences multiple AEs (preferred terms) within the same SOC then that subject will be counted only once for that SOC. When summarizing by severity and relationship, only the AE with the highest severity or relationship will be counted.

In addition to summary tables, the following listings will be produced.

- All AEs
- AEs which resulted in dose reduction or discontinuation of study drug (i.e., action taken with study drug reported as dose reduced, dose interrupted, or drug withdrawn)

Pre-existing AEs will be flagged in the listing of all AEs.

11.2. Serious Adverse Events

Serious adverse events (SAEs) will be summarized by preferred term and SOC for each treatment arm using counts and percentages. The followings summaries of SAEs will be produced.

- Incidence by SOC and PT, in alphabetical order of SOC and PT
- Incidence by PT, in decreasing frequency of PT

In addition to summary tables, a listing of SAEs will be produced.

11.3. Definition of Treatment Emergent Adverse Events and Serious Adverse Events

A treatment-emergent AE (TEAE) is any AE that is new in onset or was aggravated in severity or frequency following the first dose of study drug, up to and including the last visit of the study. Treatment emergence will be determined by comparing the AE start date/time with the actual date/time of first dose of study drug. TEAEs are defined as events with start date/time on or after the date/time of first dose of study drug. If either the AE start date or start time is unknown, treatment-emergent events will be defined based on a “Yes” response to the CRF item “Did the AE start after the first dosing?”

A Serious Adverse Event (SAE) is defined as an AE that:

- Results in death.
- Is life-threatening.
- Requires hospitalization or prolongs existing inpatient hospitalization.
- Results in persistent or significant disability or incapacity.
- Results in a congenital abnormality or birth defect.

- Is an important medical event that requires medical intervention to prevent any of the above outcomes.

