All randomized subjects will initiate study treatment the day after randomization, receive 25 days of treatment and then be followed for up to 8 weeks post-randomization (approximately 31 days post-treatment). Therefore, the duration of the study will be approximately 8 weeks post-randomization for each subject.

Study Procedures:

Prior to taking part in the trial, subjects will be provided with an informed consent document outlining study requirements and procedures. Subjects will be given adequate time to review, discuss, and decide whether they wish to participate.

Subjects providing signed informed consent will be assessed during the Screening Period to determine their eligibility for the trial. If eligible, subjects will be required to attend a clinic visit prior to randomization in order to establish a quit date that will in turn determine the date of randomization. The quit date must be 5-7 days after starting treatment and treatment must begin on the day after randomization. Subjects will be randomized 2:1 (active vs. placebo) in a blinded manner to either Arm A or Arm B, versus Arm C and similarly to either Arm D or Arm E versus Arm F. Subjects will be provided with smoking cessation counseling beginning on the clinic visit during screening prior to randomization (setting quit date and plan), again on day of randomization, and continuing at various scheduled times through the Week 8 Follow-Up Period.

Compliance will be assessed during the treatment period by reviewing subject's diary (date and time of dosing) as well as ongoing drug accountability at each clinic visit (Days 2, 3, 6, 12, 16, 20, and 27).

Subjects will be assessed for efficacy (number of cigarettes smoked daily during treatment as well as smoking cessation status by self-report of abstinence with biochemical verification (expired CO) during the follow-up assessments at Week 5, 6, 7 and 8).

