7.3.2. Efficacy Objectives

Cytisine was developed and is being marketed using a 25-day titration treatment schedule for smoking cessation using a 1.5 mg dose. The primary efficacy objective of this Phase 2b trial is to assess the overall reduction in daily cigarette smoking during the study treatment dosing/schedules compared to the respective placebo arms (i.e. the marketed titration schedule or a simplified tid schedule). Reduction in daily cigarette smoking was chosen as the primary efficacy outcome in order to better define the effects of the different dosing and schedules during the study treatment when such factors might have different daily effects on smoking behavior. A more simplified tid schedule was selected based on the pharmacokinetic profile for cytisine. In a recent pharmacokinetic trial (ACH-CYT-01), the geometric mean elimination half-life of cytisine (in the presence of food following administration of a 3 mg dose) was 4.63 h, but with a coefficient of variation of 24.3%. Given this variability, a tid administration schedule was chosen in order to ensure that subjects with a half-life at the lower end of the expected range will have adequate plasma concentrations of cytisine throughout the day.

Other efficacy results from this study will be used for defining Phase 3 sample size calculations when using the planned behavioral support and timing of study evaluations for the Phase 3 primary endpoint of abstinence from Week 5 to Week 8 post-randomization.

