12. STUDY PROCEDURES

After providing signed informed consent, all subjects will be evaluated for inclusion in the study within a 28 day Screening Period. Subjects who meet inclusion criteria will be required to provide a quit date that must be 5-7 days after the start of treatment and agree to initiating study treatment the day after randomization. Both planned quit and treatment start dates must be documented to confirm inclusion. Once all eligibility criteria are confirmed, randomization can occur. Study Day 1 will be defined as the first day of treatment. Subjects will complete a clinic visit on Day 2, 3, 6, 12, 16, 20 (during treatment), Day 27 (End-of-Treatment [EOT] visit), and again at the Week 5, 6, 7 and 8 visits.

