16.4. Safety Objective

Safety assessments include reported adverse events, laboratory tests results, and vital signs.

The profiles of adverse events for the arms with regard to incidences of treatment emergent adverse events will be assessed. Treatment emergent adverse events are defined as those events that appear during treatment or are present before treatment and subsequently worsen.

Laboratory, vital signs, and adverse event data will primarily be assessed for clinical safety. Data will be listed and summarized for each treatment according to measurement time.

Adverse events will be coded using the MedDRA dictionary. Coding includes system organ class (SOC) and preferred term (PT). All verbatim descriptions and coded terms will be listed for all AEs.

Safety summaries are described in the SAP.

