1. INTRODUCTION

The purpose of this Statistical Analysis Plan (SAP) is to provide a thorough description of statistical methods and presentation of the study data to be used for the analysis of data generated from the clinical trial described in protocol ACH-CYT-09: “A Multicenter, Double-blind, Randomized, Placebo-controlled Phase 2b Trial of Cytisine in Adult Smokers”, Version 2.0 (26-September-2018).

This SAP was prepared by [REDACTED] under the direction of the study sponsor, Achieve Life Sciences Inc. (Achieve). It includes details of data handling procedures and statistical methodology. The final statistical analyses will proceed in accordance with this SAP as approved by both Achieve and [REDACTED]. Any deviation from this SAP will be documented in the final CSR. Any deviations from methods described in the protocol are also detailed and explained in this SAP.

For this study, [REDACTED] is responsible for programming of datasets. [REDACTED] will provide to Achieve the Study Data Tabulation Model (SDTM) as well as Analysis Data Model (ADaM) dataset specifications based on:

- SDTM Model 1.4 and SDTM Implementation Guide (SDTM IG) version 3.2.
- ADaM Model 2.1 and ADaM Implementation Guide (ADaM IG) version 1.1.

In addition to the protocol, the following documents were reviewed in preparation of this SAP:

- Electronic Case Report Form (eCRF) version 2.1, 27-Feb-2019
- eCRF Completion Guidelines version 1.1, 28-Feb-2019
- Data Management Plan version 1.0, 05-Sep-2018
- Study Design Specification version 2.1, 27-Feb-2019

[figure not shown]

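### SAP 11.3 counts adverse events as treatment-emergent through Week 8, the protocol limits new onsets to treatment, and no listed table separates the two periods

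*SAP*

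**What the plan says.** Protocol 16.4, repeated in the synopsis, reads: "Treatment emergent adverse events are defined as those events that appear during treatment or are present before treatment and subsequently worsen". It gives no calendar day for the end of treatment in this sense, and the part on pre-existing conditions that worsen has no stated end.

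SAP 11.3 sets the window as "following the first dose of study drug, up to and including the last visit of the study". Its working rule is "TEAEs are defined as events with start date/time on or after the date/time of first dose of study drug", which has no upper limit. SAP 6.2 defines a Study Treatment Period ending at the Day 27 end-of-treatment (EOT) visit and a separate Follow-up Period for Weeks 5 to 8, but SAP 11 does not use that division for adverse events.

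The SAP Introduction states: "Any deviations from methods described in the protocol are also detailed and explained in this SAP". Neither SAP 11.3 nor SAP 13 mentions the TEAE window.

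SAP 11.1 and the list of tables give TEAE summaries overall, by system organ class (SOC) and preferred term (PT), by relationship and severity, and for events leading to dose reduction or discontinuation. None of the titles or descriptions splits events by treatment period. The table shells are blacked out, so this rests on the titles and the text of 11.1.

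**The concern.** The safety objective is to compare the profiles of two doses and two schedules with placebo, and SAP 6.5 makes adverse events a key study endpoint. Dosing lasts 25 days and the counting window about 56. Protocol 7.3.2 reports that "the geometric mean elimination half-life of cytisine (in the presence of food following administration of a 3 mg dose) was 4.63 h", so carry-over can account for about a day after the last dose but not for a month.

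Late onsets are then a mix of background illness, relapse to smoking and nicotine withdrawal. Protocol 3.2.2 says that most reported effects of the marketed product occur early in therapy, and that drug effects cannot be separated from withdrawal. A reader of a by-arm TEAE table could not tell which onsets occurred on drug. With about 50 active and 25 placebo subjects per comparison, a few late events can change how a preferred term looks.

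**Working it through.** **1. The plan's own figure.** "Study Day 1 will be defined as the first day of treatment", and randomization is Day 0, so Week 8 post-randomization is Day 8 × 7 = 56. The last scheduled dose is on Day 25. 56 − 25 = 31 days, which reproduces the synopsis figure of "approximately 31 days post-treatment".

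**2. Share of the window after the last dose (completer).** Share = (W − 25)/W, where W is the day of the Week 8 visit (Day 56 ± 3):
- W = 53: 28/53 = 52.8%
- W = 56: 31/56 = 55.4%
- W = 59: 34/59 = 57.6%

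**3. Allowing for carry-over.** 5 × 4.63 h = 23.2 h, about one day. Share = (W − 26)/W: 27/53 = 50.9%, 30/56 = 53.6%, 33/59 = 55.9%.

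**4. Treatment taken to end at the EOT visit (SAP 6.2).** Share = (W − E)/W, where E is the day of the EOT visit (Day 27 ± 2):
- E = 27, W = 56: 29/56 = 51.8%
- E = 29, W = 53: 24/53 = 45.3%
- E = 27, W = 59: 32/59 = 54.2%

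An EOT visit on Day 25 returns the figures in step 2.

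**5. Effect on incidences, equal off-drug rates.** The documents give no off-drug event rates, so these are assumptions. Let p_on be the risk over the 25 treatment days and p_off the risk over the next 31. Then P = 1 − (1 − p_on)(1 − p_off). If p_off is the same in both arms, the risk difference (RD) is multiplied by (1 − p_off) and the risk ratio (RR) moves toward 1.

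Take p_on = 20% active and 10% placebo, with an off-drug hazard equal to a fraction f of the placebo on-treatment hazard, so p_off = 1 − 0.9^(31f/25).
- f = 1: p_off = 12.2%. Active 1 − 0.8 × 0.878 = 29.8%; placebo 1 − 0.9 × 0.878 = 21.0%. RR 1.42, RD 8.8 points.
- f = 0.25: p_off = 3.2%. Active 22.6%; placebo 12.9%. RR 1.75, RD 9.7 points.

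Without the off-drug period, RR is 2.0 and RD 10.0 points. The same calculation over the same range of f gives:
- 15% vs 5%: RR 3.0 becomes 1.86 to 2.51; RD 10.0 becomes 9.4 to 9.8 points.
- 60% vs 40% (a figure such as any TEAE): RR 1.5 becomes 1.16 to 1.35; RD 20.0 becomes 10.6 to 17.1 points.

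**6. Off-drug rates that differ by arm.** Keep 20% vs 10% on treatment and an off-drug placebo risk of 10%, so placebo is 1 − 0.9 × 0.9 = 19%.
- Active off-drug 15%: 1 − 0.8 × 0.85 = 32%. RD rises to 13.0 points; RR is 1.68.
- Active off-drug 5%: 1 − 0.8 × 0.95 = 24%. RD falls to 5.0 points; RR is 1.26.
- Active off-drug 30%: 1 − 0.8 × 0.70 = 44%. RD rises to 25.0 points; RR is 0.44/0.19 = 2.32.

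**The case against.** The case for leaving the SAP alone has several parts.

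- **The protocol's wording is loose.** It names no end day, collects adverse events to Week 8 (Protocol 14) and leaves safety summaries to the SAP. This stands in part: collecting events to Week 8 is right and should continue. But the protocol keeps a 25-day Treatment Period apart from a Follow-up Assessment Period, so its definition cannot easily be read as running to Week 8.
- **Dilution is not shown.** A reader might infer that the drug-placebo contrasts are diluted. The documents do not support that as a fact, because they give no off-drug rates. Step 5 assumes equal rates; step 6 shows that unequal rates can move the contrast up or down. For uncommon terms the risk difference changes little.
- **Safety output is descriptive.** SAP 11 plans no statistical comparison of arms for safety, so no planned table contains the risk ratio in step 5. This stands, though readers will still compare the columns.
- **The off-drug majority is not certain.** It holds at every allowed Week 8 date when measured from the last dose, but not always when measured from the EOT visit.
- **Early stoppers.** A subject who stops on Day 5 and stays to Week 8 has 51 of 56 days (91%) off drug. Protocol 8.3.1 keeps such subjects under full evaluation deliberately, and nothing indicates how many to expect. In the 24 completed subjects of ACH-CYT-02, no TEAE led to withdrawal of drug.
- **Existing output helps somewhat.** The Kaplan-Meier figure of time to first TEAE shows onset timing, and all events are listed. But that figure covers first events of any kind, not preferred terms, and a listing is not a summary.

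**Conclusion.** The mismatch between the two definitions is plain, and the SAP does not explain it despite its own undertaking. For a completer, 55% of the window (53% to 58%) lies after the last dose, or 52% if treatment ends at the Day 27 visit (45% to 54% for an EOT visit on Day 27 to 29). The planned tables do not show the on-treatment profile that the protocol's definition describes.

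The effect on the contrast is conditional. If off-drug rates are similar across arms, relative differences are understated, by the amounts in step 5 under assumed rates. If they are not, the direction is unknown.

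Two stronger conclusions are not supported. One is that the safety comparison is known to be biased toward no difference. The other is that the protocol calls for a last-dose-plus-washout window as the main table: it states no washout, and such a window is a choice with its own drawback. The point is worth correcting because the repair is cheap and serves the safety objective directly.

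**What to change.** - **SAP 11.3:** reconcile the TEAE definition with Protocol 16.4. If the longer window is kept, say that it departs from the protocol and why.
- **SAP 11.1:** add an on-treatment TEAE summary by SOC/PT and by severity, covering onset or worsening from first dose through a pre-specified end of treatment. That end could be the SAP 6.2 Study Treatment Period, or the subject's actual last dose plus a short fixed carry-over interval. Choose one before unblinding.
- **SAP 11.1:** add a separate table of onsets after that point.
- Keep the first-dose-to-Week-8 table as the overall summary.

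The cost is SAP wording and one extra set of adverse event tables. No new data are needed: SAP 9.1 already uses first- and last-dose dates, and Protocol 14.2 records date and time of onset. One drawback should be stated in the SAP: if actual last dose is used, on-treatment observation time varies with discontinuation, which may differ by arm. The Study Treatment Period avoids most of this, but includes some off-drug days for early stoppers.

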12.2.2. Randomization

Randomization (Day 0)

Randomization must occur 5-7 days prior to the agreed upon quit date so that the actual quit date falls on Treatment Day 5, 6 or 7. All other screening evaluations must be completed within 28 days prior to the Randomization Day. Study treatment must start on the day after randomization.

Study procedures include:

1. Update concomitant medication(s).
2. Document any existing adverse event(s).
3. Vital signs, including weight.
4. Expired CO.

Upon completion of all procedures and final confirmation of eligibility, complete the following:

1. Subject to complete the following questionnaires:
 - a. Fagerström Test for Nicotine Dependence ([Appendix 2](#)).
 - b. Smoking Self-Efficacy questionnaire (SEQ-12) ([Appendix 3](#)).
 - c. Short Form of the Tobacco Craving questionnaire ([Appendix 4](#)).
 - d. HADS questionnaire ([Appendix 5](#)).
 - e. Alcohol Use questionnaire ([Appendix 6](#)).
2. Provide subject with behavioral support information that includes counseling ([Appendix 7](#)). NOTE: it should be stressed to subjects that even if they are smoking less during the study treatment, they must maintain their dosing schedule throughout the Treatment Period.
3. Randomize according to a pre-determined, blinded, randomization schedule (see Section [7.5](#)).
4. Provide study treatment medication packs #1 and #2, which contain tablets required for Days 1-2 and Days 3-4. Enter actual treatment dates on the packs next to the dosing day designation in the space provided. Review the layout and dosing instructions printed on the medication packs which cover dosing requirements, timing of study drug administration and how to remove individual tablets from the blister pack. Instruct subject that any/all packs must be brought back to the clinic and should never be thrown away.
5. Develop an appointment schedule that includes dates and times for each required clinic visit during the trial, providing copy to the subject.
6. Provide diary instructions.

7. Schedule a time on the following day (day 1 of treatment, late in the day) when clinic will contact subject to assess compliance, any possible adverse events and any changes/additions in concomitant medications.
8. Remind subject of appointment time for Day 2 clinic visit.

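### The SAP's medication rules leave some drugs taken on treatment in neither summary table, and its start-date rule for TEAEs does not apply the worsening criterion in its own definition

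*SAP*

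**What the plan says.** **Medications.** SAP 8.3 makes a medication prior if its stop date precedes first dose. SAP 11.7 opens with a broad idea of concomitant medication (any drug other than study drug used while on treatment), then equates it with a start date on or after first dose. It adds one extension: drugs begun in screening whose stop date is missing or marked ongoing. Protocol 10 says that subjects stay on their existing prescriptions, and that their regimens should be kept stable. Concomitant medications are a safety endpoint in SAP 4.2. The summaries are Table 14.1.8 (prior) and Table 14.3.4.8 (concomitant); Listing 16.2.11 covers both.

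**TEAEs.** SAP 11.3 first defines a TEAE as "any AE that is new in onset or was aggravated in severity or frequency following the first dose of study drug". Protocol 16.4 agrees, covering "those events that appear during treatment or are present before treatment and subsequently worsen". SAP 11.3 then turns this into a rule: "TEAEs are defined as events with start date/time on or after the date/time of first dose of study drug". If the start date or time is unknown, the CRF item "Did the AE start after the first dosing" decides. Pre-existing AEs are in the data. SAP 11.1 states "Adverse event reporting will start at the date of informed consent" and also "Pre-existing AEs will be flagged in the listing of all AEs", and the protocol has existing AEs documented at both screening visits and at randomization.

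**The concern.** In both places a broad definition is followed by a narrower rule, and the rule is what will be programmed.

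For medications, the drugs most likely to be in use throughout treatment are long-standing prescriptions started before screening. These are the drugs that the concomitant rule does not reach, and the prior rule does not reach them either. A reader of Table 14.3.4.8 would see an incomplete picture of what subjects were taking alongside study drug.

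For AEs, the aggravation criterion is stated but not applied. If a pre-existing AE worsens after first dose and keeps its original start date, it drops out of the TEAE tables and the time-to-first-TEAE figure. One of those tables covers TEAEs that led to dose reduction or discontinuation, a category that SAP 6.5 names among the key study endpoints. SAP 11 plans no statistical comparison of safety, so the descriptive tables carry the safety objective.

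**Working it through.** **Medications.** The plan gives no figure to reproduce, so the two rules were applied to every feasible combination of start and stop.

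- Prior (SAP 8.3): known stop < first dose.
- Concomitant (SAP 11.7): start ≥ first dose, or start in screening with stop ongoing or missing.

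| Start | Stop | On treatment? | Table |
|---|---|---|---|
| Before screening | Known, before first dose | No | Prior |
| Before screening | Known, on/after first dose | Yes | **Neither** |
| Before screening | Ongoing | Yes | **Neither** |
| Before screening | Missing | Unknown | **Neither** |
| In screening | Known, before first dose | No | Prior |
| In screening | Known, on/after first dose | Yes | **Neither** |
| In screening | Ongoing | Yes | Concomitant |
| In screening | Missing | Unknown | Concomitant |
| On/after first dose | Known, on/after first dose | Yes | Concomitant |
| On/after first dose | Ongoing | Yes | Concomitant |
| On/after first dose | Missing | Yes | Concomitant |

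There are 3 × 4 − 1 = 11 classes, because a start after first dose cannot have a stop before it. Prior 2 + concomitant 5 + neither 4 = 11. Of the four unplaced classes, three are certainly on treatment and one is of unknown status. If concomitant is instead defined as stop on or after first dose, ongoing or missing, whatever the start, the split becomes prior 2 + concomitant 9 + neither 0 = 11, with no class in both tables.

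**TEAEs.** The definition and the rule in SAP 11.3, compared over four kinds of event:

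| Event | Definition | Start-date rule |
|---|---|---|
| New after first dose | TEAE | TEAE |
| Pre-existing, unchanged | Not | Not |
| Pre-existing, worsened, original record kept | TEAE | **Not** |
| Pre-existing, worsened, entered as a new record | TEAE | TEAE |

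They disagree in one case. The CRF fallback does not help, because it too asks only about the start.

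The period in which such records can be opened is uncertain because the documents differ. Protocol 14 has AEs recorded in the CRF from randomization, and dosing starts the next day, which gives about one day. SAP 11.1 starts at consent, which gives up to 28 days of screening plus Day 0.

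An affected AE still appears in the any-AE row of the overall summary, the AE listings, the SAE tables if serious, and the SAP 7 discontinuation reasons if it led to stopping study drug. An unplaced drug should still appear in Listing 16.2.11.

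**The case against.** The best defence on TEAEs is that sites may enter each worsening as a new AE with its own start date, in which case the start-date rule loses nothing. The rule directly follows the sentence on aggravation, so its authors may have assumed this. SAP 1 cites an eCRF and Completion Guidelines that could settle the matter, but they are not among these documents. This defence stands as a reason for moderate confidence. It does not remove the contradiction, because neither the protocol nor the SAP states the convention, and Protocol 14.2 speaks of updating AE documentation as necessary.

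A reader might go further and infer that a worsening could never be recovered from the original record, since Protocol 14.2 lists one onset and no worsening date. The documents do not support that. The CRF item cited in SAP 11.3 is absent from the Protocol 14.2 list, so that list is not the whole CRF, and a worsening field may exist. Nor does the one-grade rule in Protocol 14.2.1 settle it: its own example concerns range grades, not change over time.

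On medications, it can be said that the drafter meant drugs recorded from screening onward, since SAP 8.3 notes that recording begins at the first screening visit. The rule, however, turns on when the drug was started. It is also fair that the drugs should still be listed, and that concomitant medication is a safety endpoint but not one of the key endpoints in SAP 6.5. Both points limit the consequence without closing the gap.

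**Conclusion.** The medication point holds on the text alone, with high confidence. Three classes of drug certainly taken on treatment are in neither summary table, and continuing prescriptions, which Protocol 10 expects, are among them. The fourth unplaced class should not be counted as on-treatment use, because its stop date is missing.

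The TEAE point is secondary, with moderate confidence. SAP 11.3 contradicts its own definition and Protocol 16.4, but the effect depends on the unseen recording convention.

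Neither gap can be sized in drugs, events or subjects. The class counts describe the rules, not the data. Counting the TEAE tables or summary rows that an omitted event could affect would not measure the size either, since one AE enters only a few of them. Both parts touch descriptive safety outputs only, and no efficacy analysis changes. They should be corrected because the repair is small and any queries must go out before database lock.

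**What to change.** 1. **SAP 11.7.** Define concomitant medication as any medication with a stop date on or after first dose, or ongoing, or missing, whatever its start date. Leave the prior definition in SAP 8.3 unchanged. A drug with no stop date is then concomitant by convention, which could include some drugs stopped long ago, so query missing stop dates before lock. State how partial stop dates are handled, since the safety rules in SAP 6.3.1 impute start dates only.
2. **SAP 11.3.** State that a worsening of a pre-existing AE after first dose is entered as a new AE record starting on the date of worsening. The existing start-date rule and the time-to-first-TEAE figure then work as written. If this was not already the site convention, add the instruction and query pre-existing AE records before lock.

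The cost is about one sentence in each section, the matching programming for medications, and the queries. The concomitant table will grow to include background drugs, and TEAE counts may rise slightly.
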